### **14.4 Subject information card**

The subject will be provided with a Subject Information Card including the following information:

- That he/she is participating in a clinical study
- Subject study ID
- That he is treated with the IMP/placebo
- The name and phone number of the Investigator
- Name and address of the Sponsor

#### **14.5 Subject data protection**

The ICF includes information that data will be recorded, collected and processed and may be transferred to European Economic Area (EEA) or non-EEA countries. In accordance with the European Union Data Protection Directive (95/46/EC), the data will not identify any persons taking part in the study.

The potential study subject (or the subject's legally acceptable representative and/or witness, as applicable) should be informed that by signing the ICF he approves that authorized representatives from Sponsor and CTC, the concerned IEC and CA have direct access to his/her medical records for verification of clinical study procedures. This agreement is to be substantiated in a separate document, according to local requirements.

The subject has the right to request access to his/her personal data and the right to request rectification of any data that is not correct and/or complete.

The Investigator must file a *Subject Identification List* which includes sufficient information to link records, *i.e.*, the CRF and clinical records. This list should be preserved for possible future inspections/audits but should not be made available to the Sponsor except for monitoring or auditing purposes.

#### **14.6 Changes to the approved Clinical Study Protocol**

Any proposed change to the approved Final CSP (including appendices) will be documented in a written and numbered Clinical Protocol Amendment. All amendments including substantial changes to the protocol must be approved by the appropriate IEC and/or CA before implementation according to applicable regulations.

#### **14.7 Audits and inspections**

Authorized representatives of Sponsor, a CA, or an IEC may perform audits or inspections at the research clinic, including Source Data Verification (SDV). The purpose of an audit or inspection is to systematically and independently examine all study-related activities and documents, to determine whether these activities were conducted, and data were recorded, analyzed, and accurately reported according to the protocol, ICH-GCP guidelines and any applicable regulatory requirements. The Investigator will contact the Sponsor immediately if contacted by a CA about an inspection at the center.

#### **14.8 Insurance**

Subjects will be covered under Sponsor's liability insurance policy through the Swedish Pharmaceutical insurance (*Läkemedelsförsäkringen*). Subjects will also be covered under Isofol Medical AB's liability insurance policy through "IF Skadeförsäkring AB". The certificates of insurance and an information leaflet containing essential information about the insurance coverage can be provided upon request. The participating subjects are also protected in accordance with national regulations, as applicable. CTC has a company insurance covering services performed by CTC.

## 15 STUDY MANAGEMENT

### 15.1 Training of study site personnel

Before enrolment of the first study subject a Sponsor representative or delegate will perform a study initiation visit at the research clinic. The requirements of the CSP and related documents will be reviewed and discussed and the investigational staff will be trained in any study specific procedures and system(s) utilized.

It is the responsibility of the Investigator to ensure that all personnel involved in the study are fully informed of all relevant aspects of the study, and have a detailed knowledge of and training in the procedures that are to be executed by them. Any new information of relevance to the performance of this study must be forwarded to the staff involved in a timely manner.

The Investigator will keep a list of all personnel involved in the study together with their function and study related duties delegated. A Curriculum Vitae will be available for all staff delegated study-specific duties.

### 15.2 Clinical monitoring

The study site will be periodically visited by a Monitor from an independent group at times agreed on by the Investigator and the Monitor. At the time of each monitoring visit, the function of the Monitor is to:

- provide information and support to the investigational team.
- confirm that facilities and resources remain acceptable.
- confirm that the investigational team is adhering to the CSP, applicable SOPs, guidelines, manuals and regulatory requirements.
- verify that data are being accurately and timely recorded in the CRFs and that IMP accountability checks are being performed.
- verify that data in the CRF are consistent with the clinical records (SDV) in accordance with the Monitoring Plan.
- verify that the correct informed consent procedure has been adhered to for participating subjects.
- ensure that withdrawal of informed consent to the use of the subject's biological samples will be reported and biological samples are identified and disposed of/destructed accordingly, and that this action is documented and reported to the subject.
- verify that AEs are recorded and reported in a timely manner and according to the CSP.

When the study has been completed and all queries have been resolved and the database has been locked, the Monitor will perform a close-out visit.

### 15.3 Source data document

A separate Source Data Verification List will be generated for each site before start of enrolment, specifying the location of the source of derived information appearing in the CRF.

This document must be signed by the Principal Investigator and the Monitor to confirm agreement before start of recruitment.

The paper CRF is considered source data when data is entered directly into the CRF.

The Investigator should guarantee access to source documents to the Monitor, CAs and the IECs, if required.

#### **15.4 Study agreements**

The Principal Investigator must comply with all the terms, conditions, and obligations of the Clinical Study Agreement for this study.

Agreements between Sponsor and CTC must be in place before any study-related procedures can take place, or subjects be enrolled.

#### **15.5 Study time table and end of study**

The end of the clinical part of the study is defined as the last visit of the last subject participating in the study.

The study is expected to start in Quarter 2, 2017 and to be completed by Quarter 2, 2018.

#### **15.6 Discontinuation of the study**

The Sponsor reserves the right to discontinue the study at any time, but intends only to exercise this right for valid scientific or administrative reasons.

After such a decision, the Investigator must inform all participating subjects and perform relevant assessments, preferably according to the scheme for the final assessments. All delivered and unused study products and other study materials must be returned and all CRFs completed as far as possible.

#### **15.7 Reporting and publication**

##### **15.7.1 Clinical Study Report**

A summarizing report must be submitted to the applicable CA and IEC within 12 months after completion of the study (in accordance with LVFS 2011:19, Chapter 9).

A CSR, in compliance with ICH E3; *Structure and content of Clinical Study Reports*, describing the conduct of the study, the statistical analysis performed and the results obtained, will be prepared by CTC. The CSR will be reviewed and approved by, as a minimum, the Principal Investigator, the Statistician and the Sponsor.

##### **15.7.2 Confidentiality and ownership of study data**

Any confidential information relating to the IMP or the study, including any data and results from the study, will be the exclusive property of the Sponsor. The Investigator and any other persons involved in the study will protect the confidentiality of this proprietary information belonging to the Sponsor.

### 15.7.3 Publication

The results from this study will be submitted for publication at the discretion of the Sponsor.

## 15.8 Archiving

The Principal Investigator is responsible for maintaining essential documents, (as defined in ICH E6 GCP, Section 8) for 10 years after finalization of the CSR. This includes any original source documents related to the study, the Subject Identification List (providing the sole link between named subject source records and anonymous CRF data), the original signed ICFs and detailed records of disposition of IMP.

It is the responsibility of the Sponsor to inform the Investigator/institution as to when these documents no longer need to be retained.

The Sponsor will archive the Study Master File (SMF) in accordance with ICH E6 GCP, Section 8 and applicable regulatory requirements.

## 16 DATA MANAGEMENT

### 16.1 Case Report Form

Data will be collected in paper CRFs specifically designed for this study. The Investigator or an authorized person will record subject data in the CRF in a precise and accurate manner. Abbreviations should not be used. The Investigator is responsible for the data entered and will sign off the CRF at each visit and at the end of the study. The data should be recorded as soon as they are generated. CRF entries must be made with an archive resistant pen. Any correction should be marked by a ~~strike-through~~ and the correct information should be written next to the error. All corrections must be signed and dated. Correction fluid must not be used. Only persons authorized by the Investigator are allowed to make entries to the CRF.

### 16.2 Database management plan and database design

Detailed information on data management will be described in a study-specific Data Management Plan (DMP). The person entering data into the database is not allowed to attempt any personal interpretation or to make any decisions on the data other than self-evident corrections as listed in the study-specific Data Entry Instructions or Data Handling Report. Single data entry type will be applied.

Data validation/data cleaning procedures are designed to assure validity and accuracy of clinical data. These procedures consist of manual reviewing during data entry and computerized edit checks and queries for identifying data values that are outside the allowed range, protocol violations, incomplete or inconsistent. The Data Validation Plan specifies the checks that are to be performed on subject data for the study. All study-specific and standard data validation programming will be tested in a separate testing environment prior to use on production data.

### 16.3 External data

External data may be received in electronic format or paper printout. Key variables are defined in order to uniquely identify each sample record. File and data formats are agreed with the external data provider. Any electronically transferred data must contain origin, date created, date sent and number of records at minimum.

The continuous 12-lead digital ECG data will be stored onto Secure Digital memory cards.

#### **16.4 Medical encoding**

Medical encoding will be performed by trained personnel at CTC. Adverse events and medical history verbatim terms are encoded using the Medical Dictionary of Regulatory Activities (MedDRA), latest version available when approving the DMP.

Prior and concomitant medications will be coded according to the WHO Anatomic Therapeutic Chemical classification system.

All coding will be approved by Sponsor.

#### **16.5 Database lock**

When all data have been entered, discrepancies solved and all reconciliation with the SAE database is complete, the database will be locked and the data will be analyzed and reported in a CSR.

## 17 STATISTICAL METHOD AND DETERMINATION OF SAMPLE SIZE

The principal features of the statistical analysis to be performed are described in this section. A more technical and detailed elaboration of the principal features will be presented in a separate Statistical Analysis Plan (SAP).

### 17.1 General

All statistical analysis of the study will be performed using the statistical software SAS for Windows Version 9.4. In all calculations, zero will be substituted for concentrations below the quantification limit of the assay. Data collected from all subjects will be presented in data listings. Both absolute values and change from baseline values for each subject will be given where applicable. All continuous data will be listed with the same precision as will be presented in the database. Data listings will be sorted by treatment, subject ID and time point. A missing value will be represented by an empty cell and no imputation will be made.

Continuous data will be summarized in tables using number of subjects (n), mean, median, standard deviation (SD), standard error (SE), 90% confidence interval (CI; based on a t-distribution if not otherwise stated), minimum, and maximum by study time point. Categorical data will be summarized by time point using frequencies and percentages. Percentages will be rounded to the nearest tenth. Population counts will be used as the denominator in the calculation of percentages unless otherwise specified.

### 17.2 Determination of sample size

Assuming a 1-sided 0.05 significance level and a standard deviation of 7 msec for  $\Delta QTcF$ , a total of 33 evaluable subjects who complete Modufolin® (24 subjects) and placebo (9 subjects), separately will be sufficient to achieve 82% power to exclude a prolongation of 10 msec or longer of the upper 1-sided 95% CI of the mean  $\Delta\Delta QTcF$ , assuming that the prolongation is 3 msec at the geometric mean peak Modufolin® concentration. Under the same assumptions, a total of 66 subjects (48 Modufolin® and 18 placebo) will achieve 97.5% power.

Note that this calculation is conservative, since it does not take into account any gain in precision due to the use of all data of each subject with the help of a linear mixed effects model.

### 17.3 Analysis data sets

#### 17.3.1 Full Analysis Set

The Full Analysis Set will consist of all subjects who have been randomized and received one dose of IMP/placebo.

#### 17.3.2 Per Protocol Analysis Set

The Per Protocol Analysis Set will consist of all subjects who have been randomized and completed the study period without any major protocol deviations. All protocol violations will be judged as major or minor at the clean file meeting.

### 17.3.3 Safety Analysis Set

The Safety Analysis Set will include all subjects who receive at least one dose of IMP/placebo and have at least one post-dose safety assessment.

### 17.3.4 PK Analysis Set

The PK Analysis Set will include all subjects who have evaluable plasma concentration data for Modufolin® and for whom one or more of the designated PK parameters can be determined.

### 17.3.5 QT/QTc Analysis Set

The QT/QTc Analysis Set will include all subjects in the Safety Analysis Set with measurements at baseline as well as on-treatment with at least one post-dose time point with a valid  $\Delta$ QTcF value. The QT/QTc Analysis Set will be used for the by-time point and categorical analyses in the electrocardiogram analysis.

### 17.3.6 PK/QTc Analysis Set

The PK/QTc Analysis Set will include all subjects who are in both the QT/QTc Analysis Set and PK Analysis Set with at least one pair of post-dose PK and QTcF data from the same time point. The PK/QTc Analysis Set will be used for the exposure-response analysis in the electrocardiogram analysis.

## 17.4 Electrocardiogram analysis

### 17.4.1 Baseline

For all ECG parameters, baseline is defined as the average of the measured QTc intervals from the 3 pre-dose time points (45, 30, and 15 min pre-dose) on Day 1.

### 17.4.2 QT correction methods and parameters

The QT and RR value for each beat will be used for HR correction.

Replicate ECGs will be extracted in up to 10 replicates from each nominal time point pre-specified in the protocol. The median value from each extracted replicate will be calculated, and then the mean of all available medians (minimum 3 medians) from a nominal time point will be used as the subject's reportable value at that time point.

#### QTcF:

The Fridericia's correction QTcF is defined as:  $QTcF = QT/RR^{1/3}$ .

### 17.4.3 Exposure-response analysis (Primary analysis)

The relationship between the plasma concentration of Modufolin® and change-from-baseline QTcF ( $\Delta$ QTcF) will be quantified using a linear mixed-effects modeling approach with  $\Delta$ QTcF as the dependent variable, plasma concentration of Modufolin® as the covariate, treatment (active or placebo) and time as categorical factors, and a random intercept per subject. The degrees of freedom for the model estimates will be determined by the Kenward-Rogers method. From the model, the slope (*i.e.*, the regression parameter for the

concentration) and the treatment effect-specific intercept (defined as the difference between active and placebo) will be estimated together with 2-sided 90% CI. The estimates for the time effect will be reported with degrees of freedom and SE.

The geometric mean of the individual  $C_{max}$  values for subjects in each of the active drug groups will be determined. The predicted effect and its 2-sided 90% CI for placebo-corrected change-from-baseline QTcF ( $\Delta\Delta QTcF$ ) (*i.e.*, the product with the slope estimate + treatment effect) at this geometric mean  $C_{max}$  will be obtained for each Modufolin® dose separately. If the upper bound of the 90% CI of the model predicted QTcF effect is below 10 msec at clinically relevant plasma levels of Modufolin®, it will be concluded that Modufolin® does not cause clinically concerning QTc prolongation.

The plot of the observed median-quantile Modufolin® concentrations and associated mean  $\Delta\Delta QTcF$  (90% CI) adjusted for diurnal effects together with the regression line presenting the predicted  $\Delta\Delta QTcF$  (90% CI) (as described in the publication by Tornoe et al.) will be used to evaluate the adequacy of the model fit to the assumption of linearity and the impact on quantifying the exposure response relationship. Additional exploratory analyses (via graphical displays and/or model fitting) will include accounting for a delayed effect (hysteresis) and the justification for the choice of pharmacodynamic model (linear versus nonlinear) as follows.

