### *Exposure-Response Analysis (Primary objective)*

The relationship between the plasma concentration of Modufolin® and change-from-baseline QTcF ( $\Delta QTcF$ ) will be quantified using a linear mixed-effects modeling approach with  $\Delta QTcF$  as the dependent variable, plasma concentration of Modufolin® as the covariate, treatment (active or placebo) and time as categorical factors, and a random intercept per subject. The degrees of freedom for the model estimates will be determined by the Kenward-Rogers method. From the model, the slope (*i.e.*, the regression parameter for the concentration) and the treatment effect-specific intercept

(defined as the difference between active and placebo) will be estimated together with 2-sided 90% CI. The estimates for the time effect will be reported with degrees of freedom and standard error SE.

The geometric mean of the individual  $C_{max}$  values for subjects in each of the active drug groups will be determined. The predicted effect and its 2-sided 90% CI for placebo-corrected change-from-baseline QTcF ( $\Delta\Delta QTcF$ ) (*i.e.*, the product with the slope estimate + treatment effect) at this geometric mean  $C_{max}$  will be obtained for each Modufolin® dose separately. If the upper bound of the 90% CI of the model predicted QTcF effect is below 10 msec at clinically relevant plasma levels of Modufolin® it will be concluded that Modufolin® does not cause clinically concerning QTc prolongation.

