#### Investigation of hysteresis:

If a QTc effect ( $\Delta\Delta QTcF$ ) exceeding 10 msec cannot be excluded in the by-timepoint analysis of the two highest dose groups, hysteresis, *i.e.*, difference in peak QT response and  $C_{max}$ , will be explored through visual inspection of overlaid PK and  $\Delta\Delta QTc$  time curves and through so called hysteresis loops for each dose of Modufolin® for Injection, 100 mg

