#### 17.4.4 By-time point analysis:

The analysis for QTcF will be based on a linear mixed-effects model with change-from-baseline QTcF ( $\Delta QTcF$ ) as the dependent variable, time (categorical), treatment (Modufolin® for Injection, 100 mg and placebo), and time-by-treatment interaction as fixed effects, and baseline QTcF as a covariate. Subject will be included as a random effect for the intercept. Subject dosed with placebo will be analyzed as a pooled group. An unstructured covariance

matrix will be specified for the repeated measures at post-dose time points for each subject. If the model with unstructured covariance matrix fails to converge, other covariance matrix such as autoregressive and compound symmetry will be considered. From this analysis, the least-squares (LS) mean and 2-sided 90 % CIs will be calculated for the contrast “Modufolin® versus placebo” at each dose of Modufolin® and each post-dose time point, separately.

For HR, PR, and QRS intervals, the analysis will be based on the change-from-baseline values ( $\Delta$ HR,  $\Delta$ PR,  $\Delta$ QRS). The same model will be used as described for QTcF. The LS mean, SE and 90% CI from the statistical modeling for both change-from-baseline and placebo-corrected change-from-baseline values will be listed in the tables and graphically displayed.

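### The primary exposure-response model leaves out baseline QTcF, which the by-time-point model for the same ΔQTcF includes; adding it is a cheap, optional improvement, not the correction of an error

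*Protocol*

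**What the plan says.** Section 17.4.3, the primary analysis, regresses ΔQTcF on "plasma concentration of Modufolin® as the covariate, treatment (active or placebo) and time as categorical factors, and a random intercept per subject". The synopsis repeats the list: "treatment (active or placebo) and time as categorical factors, and a random intercept per subject". Both read as complete lists of model terms, and neither contains baseline QTcF.

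Section 17.4.4 and the matching synopsis paragraph take the same dependent variable and specify "time-by-treatment interaction as fixed effects, and baseline QTcF as a covariate", besides time and treatment.

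The covariate needs no extra data. In section 17.4.1, "baseline is defined as the average of the measured QTc intervals from the 3 pre-dose time points" on Day 1.

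The sample size in section 17.2 is a simple two-group calculation: "Assuming a 1-sided 0.05 significance level and a standard deviation of 7 msec for" ΔQTcF, 24 active against 9 placebo subjects, a true effect of 3 msec and a limit of 10 msec. It concludes that this "will be sufficient to achieve 82% power to exclude a prolongation of 10 msec or longer". No correlation between baseline QTcF and ΔQTcF appears anywhere in the protocol.

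**The concern.** A change score and its own baseline are usually correlated, if only because measurement error in the baseline enters the change with opposite sign. When they are correlated, a chance difference in baseline between the arms passes into the unadjusted treatment contrast. With only nine placebo subjects such a difference is to be expected. The by-time-point analysis removes it and the primary analysis does not, and the protocol gives no reason for treating baseline in two ways.

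The stake is limited: how much of the observed baseline imbalance stays in the one estimate that is judged against 10 msec, and a small amount of precision.

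**Working it through.** **Inputs.** From section 17.2: SD of ΔQTcF 7 msec, 24 active and 9 placebo, true effect 3 msec, limit 10 msec (distance 7 msec), one-sided 0.05. The correlation r between baseline QTcF and ΔQTcF is assumed, over a range.

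**1. The plan's own figure.**
- SE = 7 × √(1/24 + 1/9) = 7 × 0.391 = 2.736 msec.
- Power = Φ(7/2.736 − 1.645) = 81.95%, which reproduces 82%.
- With a noncentral t on 31 df the unadjusted power is 80.43%. This is the reference below.

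**2. Size of the chance imbalance.** The SE of the difference in mean baseline is √(1/24 + 1/9) = 0.39 baseline SDs. The regression slope of ΔQTcF on baseline is r × 7 per baseline SD. A one-SE imbalance therefore moves the unadjusted contrast by |r| × 7 × 0.391 = |r| × 2.74 msec: 0.55 msec at |r| = 0.2 and 0.82 msec at 0.3.

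**3. Power with the covariate.** The adjusted variance is SE² × (1 − r²) × (1 + T²/31), on 30 df, averaged over the chance imbalance T (t with 31 df). The last factor charges for estimating the covariate.

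| \|r\| | Adjusted power | Change from 80.43% |
|---|---|---|
| 0 | 79.22% | −1.2 |
| 0.1 | 79.57% | −0.9 |
| 0.15 | 80.01% | −0.4 |
| 0.2 | 80.64% | +0.2 |
| 0.3 | 82.44% | +2.0 |
| 0.4 | 85.02% | +4.6 |

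Break-even is at |r| of about 0.185. Of the 1.2 points lost at r = 0, only 0.05 is the lost degree of freedom (80.43% to 80.38%); the rest is the variance of estimating the covariate. The mean half-width of the 90% CI is 4.60 msec unadjusted, and 4.68, 4.63 and 4.47 msec adjusted at |r| = 0, 0.15 and 0.3.

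**4. What |r| might be.** If the correlation comes only from regression to the mean, |r| = v / √((B² + v) × 49). Here v is the baseline error variance and B the between-subject SD of QTcF, taken as 10 to 20 msec. Two values of v are tried:
- v = 12.25: independent noise at each time point with a three-point baseline mean, so that v + 3v = 49.
- v = 24.5: half of the ΔQTcF variance.

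| v | B = 10 | B = 15 | B = 20 |
|---|---|---|---|
| 12.25 | 0.17 | 0.11 | 0.09 |
| 24.5 | 0.31 | 0.22 | 0.17 |

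Over |r| = 0.09 to 0.31 the power change is about −0.9 to +2.2 points.

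**5. Cross-check in the mixed model.** The generalised least squares SE of (treatment effect + slope × Cmax) at the top dose was computed for the section 17.4.3 model over 12 post-dose times. The concentration curve was assumed and the variances were taken as known. With half the variance between subjects, adding baseline moves the SE from 2.617 to 2.643 msec at r = 0, from 2.608 to 2.576 at 0.2, and from 2.613 to 2.505 at 0.3. A second check treated baseline error as the shared subject component in the six scenarios of step 4. The SE fell in five (for example 2.746 to 2.635, and 2.741 to 2.716) and rose by 0.004 in the sixth.

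**The case against.** The strongest reply is that nothing here is wrong. A pooled concentration regression and a per-dose, per-time contrast are different models, and no passage says that they must share covariates. The estimate is unbiased over randomisation and the interval is valid either way. This stands, and it is why the point is an improvement and not a defect.

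A second reply is that the expected gain has no clear sign. In the single-contrast framework four of the six scenarios in step 4 lie below break-even, with adjusted power of 80.2, 79.7, 79.5 and 80.2% against 80.4%. This stands for a contrast at one time point. It carries over only partly to the planned model: the mixed-model check favours adjustment in five of the six, though by small amounts. Section 17.2 also says that its power is conservative because mixed-model precision is not counted, so power alone does not make the case.

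Two stronger readings are tempting, and the documents do not support them.
- A reader might infer that the difference undermines the hysteresis check, because that check starts when an effect "exceeding 10 msec cannot be excluded in the by-timepoint analysis of the two highest dose groups". But the protocol never compares the primary estimate with the by-time-point estimate. Hysteresis is explored by inspecting plots, and adding baseline to the primary model would change neither the trigger nor those plots.
- A reader might infer that the two planned analyses will often disagree on 10 msec because of baseline handling. Comparing one contrast with and without the covariate does not show this. The planned models also differ in dose pooling, linearity in concentration, the interaction term and covariance structure, all of which would remain.

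**Conclusion.** The point holds as a low-priority, optional improvement. The primary model omits a covariate that is already collected and that the companion model for the same variable uses, without a stated reason. Including it takes the observed baseline imbalance out of the primary ΔΔQTcF estimate: about 0.5 to 0.8 msec for a one-SE imbalance at |r| of 0.2 to 0.3. It brings a small precision gain if the correlation is large enough.

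The size rests on an assumed correlation. For |r| of 0.09 to 0.31 the power change is about −0.9 to +2.2 points in the plan's own framework, and at zero correlation it is a loss of about 1.2 points. The power figures are single-contrast calculations, and the mixed-model check uses an assumed concentration curve and known variances. The SAP is not at hand and may already add the term.

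The documents do not support calling the primary analysis biased or its interval invalid, and the 82% does not depend on this term.

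**What to change.** In section 17.4.3 and the matching synopsis paragraph, add baseline QTcF, centred at the overall mean, as a fixed covariate in the primary exposure-response model. Centring leaves the ΔΔQTcF contrast unchanged and keeps the time estimates readable at an average baseline.

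Because this changes the pre-specified primary model, make it by documented amendment before unblinding, so that nobody chooses between the two versions after seeing results.

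Cost: no new data, subjects, margin or decision rule. The named downside is about 1.2 power points (80.4% to 79.2%) if baseline and ΔQTcF turn out to be uncorrelated.
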